Open label with 30-day run-in phase to establish baseline parameters and a 90-day withdrawal phase to determine duration of treatment response.

Study duration

Run-in phase: 1 month Treatment phase: 3 months Withdrawal phase: 3 months

Planned number of

subjects

Approximately 20 subjects

Protocol EPI589-15-001 Version: Amendment 2.0

Test product, mode of administration, strength, and dose

Test Product

EPI-589 in a tablet formulation at a strength of 250 mg

Mode of Administration

Oral with food

Dose

EPI-589 500 mg BID

Reference therapy (for controlled studies)

None

Safety monitoring

Clinical

- 1. Physical exam and vital signs
- 2. Evaluation of adverse events
- 3. 12-lead Electrocardiogram
- 4. Columbia Suicide Severity Rating Scale (C-SSRS)

Laboratory

- 1. Routine serum chemistries
- 2. Routine hematology tests and coagulation tests

Inclusion Criteria

- 1. Diagnosis of possible, probable, laboratory supported probable or definite amyotrophic lateral sclerosis (ALS) by El Escorial Criteria
- 2. or between 21 and 70 years of age
- 3. Forced vital capacity (FVC) \geq 70% of predicted
- 4. Onset of weakness within 3 years as documented in clinical records
- 5. Agreement to use contraception if within reproductive years
- 6. Willingness and ability to comply with study procedures
- 7. Stable regimen of dietary supplements for 30 days prior to enrollment
- 8. Abstention from use of other investigative or non-approved drugs
- 9. Subjects on riluzole must be on a stable dose for at least 30 days prior to study enrollment.
- 10. Subject must be able to swallow 0.375 x 0.700 inch tablets.

Exclusion Criteria

- 1. Allergy to EPI-589
- 2. Use of invasive or non-invasive ventilation
- 3. Participation in other intervention studies
- 4. Diagnosis of any other neurologic disease
- 5. Malignancy within past two years
- 6. Pregnant or plans to become pregnant

- 7. History of stroke
- 8. History of brain surgery
- 9. Hepatic insufficiency with liver function tests (LFTs) greater than three times upper limit of normal (ULN)
- 10. Renal insufficiency requiring dialysis
- 11. End stage cardiac failure
- 12. Participation in a trial of a device, drug or other therapy for ALS within 3 months of screening and for the duration of the trial

Treatment

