Blood-based glutathione cycle biomarkers		✓	✓	✓		✓	✓		✓
Urine-based biomarkers		✓	✓	✓		✓	✓		✓
Lumbar puncture (CNS)			✓			✓			
ALSFRS-R		✓	✓	✓		✓	✓		✓
Water and solid swallowing tests			✓			✓			✓
Speech assessment			✓			✓			✓
Handheld dynamometry			✓			✓			✓
AE/SAE Assessment			✓	✓	√e	✓	✓	√e	√ g
Drug plasma concentration ^f				√f		√f			
Concomitant medications	✓		✓	✓	√e	✓	✓	√e	√ g
Dosing Schedule				Month 1	Month 2	Month 3			
EPI-589 BID				✓	✓	✓			

- a. Height measurement need not be repeated after treatment begins.
- b. Physical examination includes breast examination in women at screening.
- c. Urine or Serum pregnancy test will be done for of child bearing potential only.
- d. Run-in assessments must be performed 30 Days (+/- 3 days) prior to baseline after confirmation of eligibility and enrollment in the study.
- e. Month 2 assessments and Withdrawal Phase Month 5 assessments can be conducted by telephone.
- f. Samples will be collected at 0-hour and 0.5, 1, 2, 4, 6, 8, and 12 hours post-dose on study visit days. 12 hour PK can be obtained at time 0.
- g. AEs reported at Month 6 (and any associated concomitant medications) must be followed for 30 days; this follow-up may be conducted by telephone
- h. Screening values can be used if done within one month of baseline and if completed under fasted conditions

Version: Amendment 2.0

III. BACKGROUND INFORMATION AND RATIONALE

A. Overview of Amyotrophic Lateral Sclerosis (ALS)

Amyotrophic lateral sclerosis (ALS) is a fatal neurodegenerative disease without an effective therapy. ALS causes progressive damage and loss of motor neurons in the central and peripheral nervous systems that result in a gradual decrease and loss of motor and brainstem function. ALS is estimated to occur in 1–2/100,000 people worldwide. The majority of ALS cases are sporadic, however about 10% of cases are inherited (familial ALS), with 20% of familial ALS resulting from mutant forms of the superoxide dismutase soluble gene (SOD1), a homodimer that converts superoxide radicals to molecular oxygen in mitochondrial membranes and cytoplasm. Symptoms of motor neuron death in sporadic and familial ALS are clinically indistinguishable. The role of oxidative stress (OS) and mitochondrial dysfunction as key pathophysiological features in all forms of ALS has been well established.¹

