In MAD study EPI589-14-001, EPI-589 was rapidly absorbed following oral administration and the median C_{max} was attained within 1 hour (0.50 to 0.76 hours) under fasted conditions after single or multiple dosing among these five cohorts. The mean half-life of EPI-589 ranged from 5.64 to 8.47 hours among these five cohorts. In general, the mean values of the time to peak concentration (T_{max}), half-life ($t_{1/2}$), apparent terminal constant (λz), accumulation ratio (AR), percent fluctuation (%F) and accumulation index (AI) of EPI-589 were similar among the five cohorts.

It appears that no significant effects of age and smoking on EPI-589 pharmacokinetics were observed in this study.

Dose proportionality existed in the exposures (AUC_{0-tau}, C_{max}, C_{min} and C_{avg}) over the dose range of 250 to 500 mg BID EPI-589 under fasted conditions.

F. Clinical Study

EPI589-15-001: A Phase 2A Safety and Biomarker Study of EPI-589 in Subjects with Amyotrophic Lateral Sclerosis.

G. Selection of Drugs and Dosages

The study drug in this trial is EPI-589 (common chemical name (R)-troloxamide quinone).

Each tablet contains 250 mg of EPI-589. The study dose is 500 mg BID, to be maintained in the absence of treatment-emergent toxicity. EPI-589 tablets must be taken with food.

H. Number of Subjects to Enroll in Study

Approximately 20 subjects with ALS.

I. Compliance Statement

This study will be conducted in full accordance with all applicable research policies and procedures, all applicable US federal and local laws and regulations including 45 CFR 46, 21 CFR Parts 50, 54, 56, 312 and 314, and the Good Clinical Practice: Consolidated Guideline approved by the International Conference on Harmonization (ICH). Any episode of noncompliance will be documented.

The investigators will perform the study in accordance with this protocol, obtain consent and report AEs in accordance with local institutional policies and procedures and all EU and US federal requirements. Collection, recording, and reporting of data will be accurate and will ensure the privacy, health, and welfare of research subjects during and after the study.

J. Relevant Literature and Data

Literature references have been provided in Section XV. Additional information can be found in the Investigator's Brochure.

IV. STUDY OBJECTIVES

A. Primary Objective

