The primary objective is to evaluate the effects of EPI-589 on safety as assessed by occurrence of drug-related serious adverse events in subjects with ALS.

B. Secondary Objectives

The secondary objectives are to evaluate the effects of EPI-589 in subjects with ALS on:

- 1. Glutathione cycle biomarkers as measured in blood, cerebral spinal fluid, and urine
- 2. Disease progression as assessed by ALS Functional Rating Scale-Revised
- 3. Respiratory function as assessed by pulmonary function tests and capnography
- 4. Failure to thrive as measured by body weight
- 5. Swallowing as assessed by change in water and solid swallowing tests
- 6. Speech as assessed by speech evaluation
- 7. Muscle function as assessed by handheld dynamometry
- 8. Drug plasma concentration measurements
- 9. Hematology, blood chemistry, electrocardiogram

V. INVESTIGATIONAL PLAN

A. General Schema of Study Design

After study enrollment, baseline assessments will be performed. Subjects participate in a 30-day run-in phase to establish baseline ALS disease-related clinical and biomarker features. EPI-589 will then be administered for 3 months, unless discontinued for safety or tolerability issues. All subjects will then be followed for an additional 90 days to determine long-term effects, duration of response to treatment, and potential effects of EPI-589 therapy on known disease trajectory.

A1. Screening Phase

Suitable candidates for the trial will receive a short overview of the study by the Investigator's staff and, if interested, will undergo Screening. The Investigator will inform each prospective subject of the nature and details of the study, explain the potential risks and must obtain written informed consent from the subject or their legally authorized representative prior to performing any study related procedures.

A2. 30-Day Run-in Phase

Once eligibility is confirmed, the subject will be enrolled in the study and the ALS Functional Rating Scale-Revised (ALSFRS-R) measurements and CNS, urine-based and blood-based glutathione cycle biomarkers, will be collected.

A3. Baseline

ALSFRS-R, lumbar puncture, swallowing, speech, handheld dynamometry, blood-based biomarkers, urine biomarkers, and clinical measurements will be collected.

A4. Treatment Phase

EPI-589 dosing will start on Day 1. Subjects will self-administer EPI-589 at a dose of 500 mg BID.

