Blood biomarker, urine biomarker, clinical measurements, and pharmacokinetic plasma concentrations will be collected at Day 29 (+/-3 days) and Day 85 (+/- 3 days). Lumbar puncture will be collected at Day 85 (+/- 3 days).

A5. Study Withdrawal Phase

Closeout data will be collected over a 90-day period, during the Withdrawal Phase.

ALSFRS-R, blood-based biomarkers, urine-based biomarkers, and physical exam including weight and vital signs will be collected at Month 4.

ALSFRS-R, swallowing, speech, handheld dynamometry, blood-based biomarkers, urine-based biomarkers, and physical exam including weight and vital signs will be collected at Month 6.

Adverse events reported as ongoing during the Withdrawal Phase, and any concomitant medications associated with such events will be followed for 30 days. Month 5 AE and concomitant medication assessments can be conducted by telephone.

B. Randomization and Blinding

This is an open-label study.

C. Study Duration, Enrollment and Number of Sites

C1. Duration of Subject Treatment

Subjects will participate in a 30-day run-in phase to establish baseline ALS disease-related clinical and biomarker features. EPI-589 will then be administered for 3 months unless discontinued for safety or tolerability issues. Subjects will return to the clinic for assessments at two time points during a 90-day withdrawal period.

C2. Total Number of Study Sites/Total Number of Subjects Projected

This study will be conducted at the California Pacific Medical Center, San Francisco, CA. Additional sites may be added in order to decrease enrollment timelines.

Projected enrollment is approximately 20 subjects with ALS.

D. Study Population

D1. Inclusion Criteria

- 1. Diagnosis of possible, probable, laboratory supported probable or definite amyotrophic lateral sclerosis (ALS) by El Escorial Criteria.
- 2. Male or female between 21 and 70 years of age
- 3. Forced vital capacity (FVC) \geq 70% of predicted
- 4. Onset of weakness within 3 years as documented in clinical records
- 5. Agreement to use contraception if within reproductive years
- 6. Willingness and ability to comply with study procedures
- 7. Stable regimen of dietary supplements for 30 days prior to enrollment
- 8. Abstention from use of other investigative or non-approved drugs
- 9. Subjects on riluzole must be on a stable dose for at least 30 days prior to study enrollment.
- 10. Subject must be able to swallow 0.375 x 0.700 inch tablets.

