D2. Exclusion Criteria

- 1. Allergy to EPI-589
- 2. Use of invasive or non-invasive ventilation
- 3. Participation in other intervention studies
- 4. Diagnosis of any other neurologic disease
- 5. Malignancy within past two years
- 6. Pregnant or plans to become pregnant
- 7. History of stroke
- 8. History of brain surgery
- 9. Hepatic insufficiency with liver function tests (LFTs) greater than three times upper limit of normal (ULN)
- 10. Renal insufficiency requiring dialysis
- 11. End stage cardiac failure
- 12. Participation in a trial of a device, drug or other therapy for ALS within 3 months of screening and for the duration of the trial.

VI. STUDY PROCEDURES

A. Screening (-30 days \pm 3 days) Visit

A1. Screening

The Investigator will inform each prospective subject of the nature of the study, explain the potential risks, and obtain written informed consent from the subject prior to performing any study-related procedures and prior to the administration of study drug. Screening evaluations consist of the following:

- 1. Assessment of eligibility
- 2. Medical history, chart review
- 3. Physical examination (including breast examination for women)
- 4. Height, weight and vital signs
- 5. Receipt and review of all previous testing
- 6. 12-lead ECG
- 7. Pulmonary function assessment
- 8. Hematology including coagulation, serum chemistry, urine analysis
- 9. Pregnancy test (women of childbearing potential must have a negative serum or urine pregnancy test)
- 10. Concomitant medication assessment (last 60 days prior to enrollment)

A2. Run-in Assessments

Run-in assessments must be performed 30 days (+/- 3 days) prior to baseline after eligibility is confirmed and subject is enrolled in the study. Run-in evaluations consist of the following:

- 1. ALS Functional Rating Scale-Revised
- 2. Blood-based glutathione cycle biomarkers
- 3. Urine-based glutathione cycle biomarkers

B. Treatment Phase

If the subject is eligible for the study following all screening procedures and is still willing to participate in the study, the subject must return to the clinic 30 days (+/- 3 days) for baseline assessments. In-clinic study visits are scheduled at Month 1 and Month 3. Month 2 assessments can be conducted via telephone. End of treatment will be at the Month 3 study visit. Pharmacokinetic sampling takes place at Month 1 and Month 3.

B1. Baseline Assessments

The following will be assessed or performed at this visit:

- 1. Physical examination

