In this subject-controlled, open label study the incidence of drug related SAEs in addition to changes from baseline to Month 3 for disease-relevant peripheral and CNS biomarkers as well as clinical measures will be calculated for each subject. In addition, changes in the ALSFRS-R will be measured three months following withdrawal of therapy and compared with disease natural history data to determine effects of EPI-589 on disease trajectory.

A1. Analysis Populations

Demographic characteristics and baseline efficacy data will be presented and summarized for all subjects in the efficacy intent-to-treat (EITT) population. Demographic information will also be summarized for the safety population. No formal statistical comparisons will be made for either the EITT or Safety populations.

B. Efficacy Analysis

B1. Efficacy Variables

The efficacy variables in this study are

- 1. Blood-based glutathione cycle biomarkers
- 2. Urine-based glutathione cycle biomarkers
- 3. Disease progression as assessed by ALS Functional Rating Scale-Revised
- 4. Respiratory function as assessed by pulmonary function tests and capnography
- 5. Failure to thrive as measured by body weight
- 6. Swallowing as assessed by change in water and solid swallowing tests
- 7. Speech as assessed by speech evaluation
- 8. Muscle function as assessed by handheld dynamometry
- 9. Drug plasma concentration measurements

C. Safety Analysis

The primary objective of this study is to evaluate the effects of EPI-589 safety as assessed by occurrence of drug-related serious adverse events in subjects with ALS. Assessment of safety will include calculating the overall number of subjects (by absolute number and percentage) with a particular AE. Safety will also be evaluated through examining clinical laboratory data (including chemistry and hematology and coagulation information) and physical examination findings, including vital signs obtained throughout the course of the study. A medical monitor will provide study oversight.

D. Sample Size

Approximately 20 subjects will be enrolled in this exploratory biomarker study.

IX. STUDY MEDICATION

A. Description

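### For blood and urine biomarkers, Section VIII.A names only the Day 0 to Month 3 change, which cannot separate drift from drug effect or show duration of response; the samples already scheduled can address both.

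*Protocol*

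**What the plan says.** Section VIII.A (Statistical Analysis) states that "changes from baseline to Month 3 for disease-relevant peripheral and CNS biomarkers as well as clinical measures will be calculated for each subject". Its next sentence describes an analysis three months after withdrawal of therapy, for ALSFRS-R only, against natural history data.

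The sampling is richer than that. The Section II row "Blood-based glutathione cycle biomarkers" and the matching urine row are ticked at six visits:

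- **Run-in.** Section VI.A2: "Run-in assessments must be performed 30 days (+/- 3 days) prior to baseline after eligibility is confirmed". Blood and urine markers are on its list.
- **Day 0.** Section V.A3: "handheld dynamometry, blood-based biomarkers, urine biomarkers, and clinical measurements will be collected".
- **Months 1 and 3.** Section V.A4 sets these at Days 29 and 85.
- **Month 4** (Day 113, off drug). Section V.A5: "ALSFRS-R, blood-based biomarkers, urine-based biomarkers, and physical exam including weight and vital signs will be collected at Month 4".
- **Month 6** (Day 169, off drug). Sections V.A5 and VI.C.

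The Synopsis gives the reason for the outer phases: "Open label with 30-day run-in phase to establish baseline parameters and a 90-day withdrawal phase to determine duration of treatment response". Section III.B gives confirmation of target engagement, through peripheral and CNS glutathione markers, as the study's purpose. There is no control arm, and VIII.A describes the study as subject-controlled.

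**The concern.** In a subject-controlled study, the off-drug samples are the control. The one biomarker contrast that VIII.A names uses a single off-drug sample (Day 0) and a single on-drug sample (Month 3). Anything that moves the marker over those 85 days is counted as drug effect. The protocol itself links ALS to glutathione depletion, so a downward trend could hide a real effect, and a shift in the assay could imitate one. A marker that rises on drug and falls back off drug is much harder to explain by drift, but the named contrast does not look at what happens off drug.

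The same contrast cannot inform duration of response, which is the Synopsis's stated reason for the withdrawal phase. At stake is a misread target-engagement result. No formal error rate is involved.

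**Working it through.** The protocol gives no effect size, SD, power or alpha for the biomarkers, so there is no planned figure to reproduce.

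**Inputs.** Sample days are -30, 0, 29, 85, 113 and 169 (Sections II, V and VI). N is about 20 (VIII.D). Assumed, not in the documents: linear drift of b per day, a constant drug step d at Days 29 and 85, no effect left at Months 4 and 6, and independent errors with within-subject SD of 1.

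**Named contrast.** Expected value: d + 85b. Two time points cannot estimate three quantities (subject level, drift, drug step). The SE per subject is √(1 + 1) = 1.41, or 1.41/√20 = 0.316 for 20 subjects.

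**If baseline meant the mean of run-in and Day 0.** Its midpoint is Day -15, so the contrast would carry 85 + 15 = 100 days of drift. That reading does not help.

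**Size of the bias for assumed drift** (drift per 30 days × 85/30):

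| Drift, SD per 30 days | Bias, SD |
|---|---|
| 0.05 | 0.14 |
| 0.1 | 0.28 |
| 0.2 | 0.57 |
| 0.3 | 0.85 |

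At 0.1 the bias is already close to the SE of 0.316 for 20 subjects.

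**What the withdrawal samples add.** Month 3 to Month 6 spans 169 - 85 = 84 days and has expected value -d + 84b. Set beside d + 85b, the drift term keeps its sign and the drug term reverses. Half the difference of the two is d + 0.5b. Month 3 to Month 4 spans 28 days: -d + 28b.

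**Six-sample analysis** (subject effect, linear time, on-drug term):

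- Mean day = 366/6 = 61. Sum of squared deviations = 27,970.
- On-drug indicator, centred sum of squares: 2 - 4/6 = 1.333.
- Cross-product with time: (29 + 85) - 2 × 61 = -8.
- Information on d after removing drift: 1.333 - 64/27,970 = 1.331.
- SE = 1/√1.331 = 0.87 per subject, or 0.194 for 20 subjects, with linear drift removed.

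**Variations.** With Month 4 free to carry over, the SE is 0.92. With only the four samples up to Month 3 it is 1.89. Most of the information on drift therefore comes from the withdrawal samples.

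**The case against.** The strongest reply is that VIII.A is short and says only that these changes will be calculated. It does not say that nothing else will be, and visit-level modelling is commonly left to a statistical analysis plan, which is not shown here. A reader might infer that four of the six samples go unused, or that drift and drug effect are inseparable in this trial. The documents support neither. No passage says the samples are discarded, the outer phases have a stated purpose, and the confounding lies in the named contrast, not in the data collected. What remains is that the protocol does choose one biomarker contrast and does assign withdrawal data to ALSFRS-R, and that choice does not match the stated aims.

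A reader might also infer that an on-drug minus off-drug contrast should replace the Day 0 to Month 3 change. That goes too far, because any six-sample analysis rests on its own assumptions:

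- **Shape of drift.** The six-sample weights on Days -30 to 169 are about -0.270, -0.264, 0.494, 0.506, -0.239 and -0.227. Applied to squared days they sum to about -5,716, against 85² = 7,225 for the named contrast. If drift is quadratic from Day 0, -0.79 of the bias remains, with its sign reversed.
- **Persisting effect.** If the effect lasts fully through Month 6, the on-drug term returns 0.494 + 0.506 - 0.239 - 0.227 = 0.53 of it. The protocol reports that "The mean half-life of EPI-589 ranged from 5.64 to 8.47 hours among these five cohorts", so Month 4 is 28 × 24 = 672 hours, or 79 to 119 half-lives, after treatment ends. That is plasma clearance in healthy subjects, and it does not establish that the biomarker has returned to its pre-treatment level.
- **Slow onset.** If the Month 1 effect is half the Month 3 effect, the term returns 0.494/2 + 0.506 = 0.75 of the Month 3 effect.
- **Missing visits.** Subjects who stop early may have no off-drug samples.

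Finally, the documents give no longitudinal drift in blood or urine markers. The cited glutathione deficit is a cross-sectional brain imaging comparison with healthy volunteers.

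**Conclusion.** The point holds as an inexpensive improvement. For blood and urine markers, the one named contrast carries 85 days of drift that it cannot separate from a drug effect, and it leaves duration of response unaddressed. Under linear drift, wash-out by Month 4, similar effects at Months 1 and 3 and independent errors, the scheduled samples identify both drift and drug effect. The SE per subject is about 0.87 within-subject SD, against 1.41, a ratio of 0.61.

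The bias figures are a range under assumed drift. Biomarkers are secondary in an exploratory study of about 20 subjects with no formal comparisons, and the primary safety objective is unaffected. The drift-adjusted analysis belongs beside the simple change and should not replace it.

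**What to change.** In Section VIII.A, keep the per-subject Day 0 to Month 3 change. It stays the only contrast for CSF, since Section II schedules lumbar puncture at Day 0 and Month 3 only. For blood and urine markers, add:

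- **(a)** the Month 3 to Month 4 and Month 3 to Month 6 changes, reported as off-drug reversal and duration of response;
- **(b)** a within-subject repeated-measures analysis of all six samples with a subject effect, linear time and an on-drug term, using all available visits, with a sensitivity version that allows carry-over at Month 4.

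State that target engagement will be read from the three together, and list the assumptions of (b): roughly linear drift, similar effect at Months 1 and 3, and no effect persisting to Month 6.

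The cost is a few sentences and a little more analysis, with no new sample, visit or subject. The downside is that (b) can mislead if its assumptions fail, which is why the simple change and the reversal are reported alongside it.
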